	Appendix 10.2	
Section to be changed		
Description of change		
Rationale for change		
Kationale for Change		
Section to be about 1		
Section to be changed		
Description of change		
Rationale for change		
Section to be changed		
Description of change		

c17895778-08

217895778-08 Clinical Trial Protocol Page 161 of 165
Proprietary confidential information © 2023 Boehringer Ingelheim International GmbH or one or more of its affiliated companies

Dadianala fan alasas		
Rationale for change		
Section to be shought	5.5	
Section to be changed		
Description of change	Text updated from "Leftover nucleic acids from	
	patient's plasma (e.g. cfDNA) to "Leftover from	
	patient's plasma"	
Rationale for change	Updated for clarity as samples are not limited to	
	nucleic acids.	
	(0)	
Section to be changed	6.2.1	
Description of change	Added details and figure for screening visits for	
	Phase Ib PDAC patients	
Rationale for change	Addition of PDAC cohort	
Section to be changed	7.1	
Description of change	The following text was deleted "Details will be	
	specified in the TSAP".	
Rationale for change	Updated for consistency.	
Section to be changed	7.6	
Description of change	Number of cohorts updated from four to five.	
	Number of patients for Phase Ib updated from 60	
	to 80.	
Rationale for change	Addition of PDAC cohort	
Section to be changed	7.7	
Description of change	The following text in the first paragraph was	
	updated from "In total, approximately up to 12	
	CRC patients are planned approximately 60 for	
	phase Ib)" to "In total, approximately up to 140	
	patients are planned approximately 60	
	evaluable CRC patients and 20 PDAC patients for	
	phase Ib)".	
Rationale for change	Updated to reflect inclusion of PDAC (non-CRC)	
	patients.	
Section to be changed	10.2	
Description of change	In	
Rationale for change	The tickbox was inadvertently included during	
	formatting	
Section to be changed	10.2	
Description of change	In	

BI Trial No.: 1412-0001 c17895778-08

Clinical Trial Protocol

Page 162 of 165

Proprietary confidential information © 2023 Boehringer Ingelheim International GmbH or one or more of its affiliated companies

	Day 8 and Cycle 5 Day 1, which is not applicable	
	for phase Ib.	
	for phase to.	
	Footnotes have been updated accordingly.	
Dationals for shange	The tickbox was inadvertently included during	
Rationale for change	,	
Castian to be about a	formatting. 10.2	
Section to be changed		
Description of change	In Tables 10.2:2 and 10.2:3, a tickbox has been	
	added at Cycle 8 to add collection of PK and	
	ADA. In addition, footnote g updated to describe	
	that in phase Ib, PK and ADA collection is be	
	performed at Cycle 14 Day 1 and at every sixth	
	cycle thereafter (e.g. Cycle 20 Day 1 pre-dose,	
D 4: 1 C 1	etc.), and at EOT.	
Rationale for change	Addition of PK and ADA samples	
	cycle beyond	
	Cycle 14 Day 1 at pre-dose.	
Section to be changed	10.2	
Description of change		
D. (1. 0. 1.		
Rationale for change	Updated for clarity	
Section to be changed	10.2	
Description of change	Visit no for Tables 10.2:2 and 10.2:3 updated	
	from 9970 to 9961	
Rationale for change	Updated for consistency with BI standards	
	36 11	
Section to be changed	Miscellaneous	
Description of change	Updated from four to five cohorts to reflect new	
	cohort added, updated patient numbers from 60 to	
	80 in phase Ib throughout document.	
Rationale for change	Addition of PDAC cohort	
Section to be changed	Miscellaneous	
Description of change	Revisions to formatting, punctuation, and/or	
	spelling.	
Rationale for change	Clarifications added as applicable to address	
	minor formatting updates that do not affect	
	protocol content and will not be listed as separate	
	changes.	

C17895778-08 Clinical Trial Protocol Page 163 of 165

Proprietary confidential information © 2023 Boehringer Ingelheim International GmbH or one or more of its affiliated companies

11.6 **GLOBAL AMENDMENT 6**

Date of amendment	17Apr2023	
EudraCT number	2018-003268-29	
EU number	2018-003208-29	
BI Trial number	1412-0001	
BI Investigational Medicinal	BI 905711	
Product(s)		
Title of protocol	A first-in-human phase Ia/b, open label,	
	multicentre, dose escalation study of BI 905711	
	in patients with advanced gastrointestinal cancers	
Global Amendment due to urgent sa	afety reasons	
Global Amendment	X	
Section to be changed	Flowcharts	
Description of change	Section amended to clarify visits, assessments and procedures that are mandatory/not mandatory for cycles ≥ 6	
Rationale for change	Recruitment in this trial was discontinued prematurely during the Phase I expansion cohort. Reduced procedures and assessments for ongoing patients to those needed for safety monitoring.	
Section to be changed	1.3	
Description of change	Added text "Based on available preliminary data from phase I clinical studies (1412.1 and 1412.3), the decision was made to terminate BI 905711 (TRAILR2/CDH17) development program. This decision is not related to any safety concerns or unfavorable benefit/risk balance, but to the lack of predictive biomarkers and the limited efficacy particularly in the context of the evolving treatment landscape for advanced CRC and other GI cancers. The purpose of CTP v7.0 is to reduce the study related activities to the minimum required to monitor patient safety and to avoid undue burden on patients."	
Rationale for change	Explain rationale for CTP v7.0	
	3.1.1	
Section to be changed	3.1.1	
Description of change	3.1.1 Added text "Recruitment in Phase Ia is complete"	

E17895778-08 Clinical Trial Protocol Proprietary confidential information © 2023 Boehringer Ingelheim International GmbH or one or more of its affiliated companies

[figure not shown]
Section to be changed	3.1.2
Description of change	Added text "Recruitment in this trial was discontinued during Phase I expansion, and no PDAC patients were enrolled in this expansion cohort."
Rationale for change	Recruitment in Phase Ib discontinued prematurely.
Section to be changed	3.3.4.3
Description of change	Updated #2: "Emergence of any efficacy/safety information with or without invalidating the earlier positive benefit risk assessment that could significantly affect the continuation of the trial."
Rationale for change	To describe discontinuation of trial without changes to benefit-risk ratio.
Section to be changed	5.1
Description of change	Updated to reflect that tumor assessments will be assessed per institutional practice, and only overall response and disease progression will be collected in the eCRF.
Rationale for change	To be consistent with flowchart revision.
Section to be changed	5.2.1, 5.2.2, 5.2., 5.2.4
Description of change	Physical examination, vital signs, safety labs, and ECGs will be done as per institutional practice.
Rationale for change	To be consistent with flowchart revision.
Section to be changed	5.3.1, 7.3.5, 7.5, 10.1
Description of change	Updated text related to PK to align with standard Phase 1 protocol language
Rationale for change	To align with standard Phase 1 protocol language
Section to be changed	5.3.2, 5.4.1
Description of change	Effective from CTP v7.0, PK, ADA, Biomarker and Optional Tumor Biopsy samples are no longer collected for ongoing patients.

RPM	Report Planning Meeting				
BLRM	Bayesian Logistic Regression Model				
CRC	Colon Rectal Cancer				
CTC	Common Terminology Criteria				
CTP	Clinical Trial Protocol				
CTR	Clinical Trial Report				
DLT	Dose Limiting Toxicities				
DM&SM	Boehringer Ingelheim Data Management And Statistics Manual				
DRA	Drug Regulatory Affairs				
DMG	Dictionary Maintenance Group				
EDC	Electronic Data Capture				
EMEA	European Agency For The Evaluation Of Medicinal Products				
FAS	Full Analysis Set				
ICH	International Conference On Harmonization				
LOCF	Last Observation Carried Forward				
MedDRA	Medical Dictionary For Regulatory Activities				
MQRM	Medical Quality Review Meeting				
PD	Protocol Deviation				
PDAC	Pancreatic ductal adenocarcinoma				
PK	Pharmacokinetics				
PPS	Per Protocol Set				
PSTAT	Project Statistician				
PT	Preferred Term				
Q1	Lower Quartile				
Q3	Upper Quartile				
SA	Statistical Analysis				
SD	Standard Deviation				
SMQ	Standardised MedDRA Query				
SOC	System Organ Class				

Boehringer Ingelheim TSAP for BI Trial No: 1412.1

c26343384-01 Page 6 of 30

TSAP for BI Trial No: 1412.1 Page 6 of 30

Proprietary confidential information © 2023 Boehringer Ingelheim International GmbH or one or more of its affiliated companies

Term	Definition / description	
TCM	M Trial Clinical Monitor	
TESS	Treatment Emergent Signs And Symptoms	
ToC	Table of Contents	
TMW	Trial Medical Writer	
TSAP	Trial Statistical Analysis Plan	

3. INTRODUCTION

As per ICH E9, the purpose of this document is to provide a more technical and detailed elaboration of the principal features of the analysis described in the protocol, and to include detailed procedures for executing the statistical analysis of the primary and secondary variables and other data.

This TSAP assumes familiarity with the Clinical Trial Protocol (CTP), including Protocol Amendments. In particular, the TSAP is based on the planned analysis specification as written in CTP Section 7 "Statistical Methods and Determination of Sample Size". Therefore, TSAP readers may consult the CTP for more background information on the study, e.g., on study objectives, study design and population, treatments, definition of measurements and variables, planning of sample size, randomization.

SAS® Version 9.4 (or later version) will be used for all analyses analyses including immunogenicity assessment..

Pharmacokinetic (PK) parameters will be calculated using Phoenix WinNonlinTM software (version 8.1 or higher, or SAS Version 9.4 (or later version).

4. CHANGES IN THE PLANNED ANALYSIS OF THE STUDY

This section is not applicable as this is the first version of the TSAP. This TSAP reflects all amendments in CTP up to and including Amendment 6.

As of March 2023 the study was terminated due to lack of efficacy signal and it was decided to produce an abbreviated report for CTR. The abbreviated CTR would include primary and secondary endpoint analyses. There would be limited analyses provided for PK and biomarkers as detailed in section 7.5 and section 7.6.

5. ENDPOINTS(S)

5.1 PRIMARY ENDPOINT(S)

The primary endpoints in Phase Ia are:

- Maximum tolerated dose (MTD) defined as the highest dose with less than 25% risk of the true DLT rate being equal or above 33% during the MTD evaluation period as determined by the BLRM defined in section 7 of the CTP. For the definition of DLTs, refer to Section 5.2.6.1.5 of the CTP.
- Number of patients with DLTs in the MTD evaluation period.

The primary endpoints in Phase Ib are:

- Objective response based on RECIST 1.1 criteria. Objective response is defined as best overall response of complete response or partial response, where best overall response is the best response recorded from the start of the study treatment until the earliest of disease progression, death or last evaluable tumor assessment and before start of subsequent anticancer therapy.
- Progression-free survival (PFS) is defined as the time from first treatment administration until tumor progression according to RECIST 1.1 or death from any cause, whichever occurs earlier.

A detailed definition of objective response and PFS is given in section 9.1.

5.2 SECONDARY ENDPOINT(S)

5.2.1 Key secondary endpoint(s)

No key secondary endpoint is defined for this study.

5.2.2 Secondary endpoint(s)

The secondary endpoints in Phase Ia:

- The following PK parameters of BI 905711 will be evaluated after the first and after the third administrations of BI 905711:
- Cmax: maximum measured concentration of BI 905711 in plasma
- AUC0-t2: area under the concentration-time curve of BI 905711 in plasma
- Objective response based on RECIST 1.1 criteria in patients with measurable disease.

The secondary endpoints in Phase Ib:

- The following PK parameters of BI 905711 will be evaluated after the first and after the third administrations of BI 905711:
- Cmax: maximum measured concentration of BI 905711 in plasma
- -AUC0-t2: area under the concentration-time curve of BI 905711 in plasma
- Number of patients with treatment-emergent AEs
- Radiological (CT Scan) tumor shrinkage, defined as the difference between the minimum post-baseline sum of longest diameters of target lesions and the baseline sum of longest diameters of the same set of target lesions according to RECIST 1.1.
- The duration of overall response is measured from the time measurement criteria are first met for Complete Response (CR)/ Partial Response (PR) (whichever is first recorded) until the first date that recurrent or progressive disease is objectively documented (taking as reference for progressive disease the smallest measurements recorded on study) according to RECIST 1.1.
- Disease control, defined as CR, PR, or stable disease according to RECIST 1.1 from the start of treatment until the earliest of progression disease, death or last evaluable tumor assessment and before start of subsequent anti-cancer therapy.

TSAP for BI Trial No: 1412.1 Page 11 of 30
Proprietary confidential information © 2023 Boehringer Ingelheim International GmbH or one or more of its affiliated companies

TSAP for BI Trial No: 1412.1 Page 12 of 30
Proprietary confidential information © 2023 Boehringer Ingelheim International GmbH or one or more of its affiliated companies

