Median duration of treatment was 30.5 days (range, 15–246) overall and 71 days (range, 15–211) in the 0.6 mg/kg group. In the CRC group, 6/26 (23%) had a best overall response of stable disease and 3 (11.5%) were progression-free for ≥4 months. In non-CRC GI cancers group 7/22 (31.8%) evaluable patients achieved best overall response of stable disease with some tumor shrinkage and 5 (22.7%) were progression-free for ≥4 months. Three of 8 patients in the 0.6 mg/kg dose group (predicted therapeutic dose), 1/8 patients in the 1.2 mg/kg and 1/8 in the 2.4 mg/kg dose groups remained progression-free at ≥4 months. Additionally, 1 CRC patients in 2.4 mg/kg dose group achieved 21.2% tumor shrinkage accompanied by a 50% decrease in tumor marker (i.e. CEA) and 2 non-CRC GI cancer patients in 0.6 mg/kg and 4.8 mg/kg dose groups achieved >10% tumor shrinkage,

in a patient from 4.8mg/kg dose group.

Page 40 of 165

Proprietary confidential information © 2023 Boehringer Ingelheim International GmbH or one or more of its affiliated companies

Median duration of treatment in non-CRC GI cancers patients was 35.5 days (range, 15–246) overall and 116.5 days (range, 15–211) in the 0.6 mg/kg group. Thirteen (13) of 22 non-CRC GI cancer patients had PDAC. Six (6/13) PDAC patients achieved best overall response of stable disease including 4 patients that remained progression-free at ≥4 months.

Safety, pharmacokinetic, and pharmacodynamic profiles, as well as preliminary antitumor activity of BI 905711 given biweekly at three dose levels (0.6 mg/kg, 1.2 mg/kg and 2.4 mg/kg) or weekly at one dose level (0.6 mg/kg), will be assessed during 1412-0001 expansion phase 1b.

For a more detailed description of the BI 905711 profile, refer to the current Investigator's Brochure (IB).

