2.1.3 Secondary endpoint(s)

Phase Ia:

- The following PK parameters of BI 905711 will be evaluated after the first and after the third administrations of BI 905711:
 - o Cmax: maximum measured concentration of BI 905711 in plasma
 - o AUC0-t2: area under the concentration-time curve of BI 905711 in plasma
- Objective response based on RECIST 1.1 criteria in patients with measurable disease.

Phase Ib:

- The following PK parameters of BI 905711 will be evaluated after the first and after the third administrations of BI 905711:
 - o Cmax: maximum measured concentration of BI 905711 in plasma
 - o AUC0-t2: area under the concentration-time curve of BI 905711 in plasma
- Number of patients with treatment-emergent AEs
- Radiological (CT Scan) tumor shrinkage, defined as the difference between the minimum post-baseline sum of longest diameters of target lesions and the baseline sum of longest diameters of the same set of target lesions according to RECIST 1.1.
- The duration of overall response is measured from the time measurement criteria are first met for Complete Response (CR)/ Partial Response (PR) (whichever is first recorded) until the first date that recurrent or progressive disease is objectively documented (taking as reference for progressive disease the smallest measurements recorded on study) according to RECIST 1.1.
- Disease control, defined as CR, PR, or stable disease according to RECIST 1.1 from the start of treatment until the earliest of progression disease, death or last evaluable tumor assessment and before start of subsequent anti-cancer therapy.

c17895778-08 Clinical Trial Protocol Page 47 of 165

[figure not shown]
Proprietary confidential information © 2023 Boehringer Ingelheim International GmbH or one or more of its affiliated companies

Page 48 of 165 Proprietary confidential information © 2023 Boehringer Ingelheim International GmbH or one or more of its affiliated companies

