7.7 DETERMINATION OF SAMPLE SIZE

No formal statistical power calculations to determine sample size were performed for this trial. In total, approximately up to 140 patients are planned (approximately 40 evaluable CRC patients and 20 non-CRC GI cancer patients for phase Ia, approximately 60 evaluable CRC patients and 20 PDAC patients for phase Ib) for this study.

For phase Ia:

Given the pre-specified possible dose levels (Table 4.1.2.1: 1) and the number of patients per dose level, approximately 28 CRC patients will be needed to complete dose escalation.

The actual number of patients will depend on the number of dose cohorts and the cohort sizes actually tested. Based on the simulation studies to evaluate operating characteristics of the BLRM (see Appendix 10.3), on average 20-36 evaluable patients are expected to be treated in the dose escalation part for safety evaluation for the model to have reasonable operating characteristics relating to its MTD recommendation.

In addition, 12 CRC patients are planned for efficacy evaluation in phase Ia. Thus, for planning purpose, a total of 40 CRC patients and 20 non-CRC patients are planned for phase Ia.

For phase Ib (Part B):

For planning purposes, up to 15 CRC patients per each dose group for up to 4 cohorts, i.e. total of up to 60 CRC patients, and up to 20 PDAC patients for the single arm cohort will be enrolled for this part.

A Bayesian Hierarchical Model (BHM) approach (R13-4803) will be used to analyze the PFS4/ORR rate based on all data from different arms. The simulation results in Table 7.7: 1 show that with the proposed sample size per arm, the BHM approach has reasonable performance under a wide range of scenarios. The probability of passing the positive boundaries under a negative scenario is well controlled per arm (<= 3%). The probability of passing the positive boundaries under a positive/mix scenario is at least 75% per arm.

c17895778-08 Clinical Trial Protocol

Page 103 of 165

Proprietary confidential information © 2023 Boehringer Ingelheim International GmbH or one or more of its affiliated companies

Table 7.7: 1 Operating characteristics of the BHM approach in dose expansion arms under different scenarios

Scenario: PFS4 (%)/ORR (%) Prob. PFS4 _{BHM} \geq positive boundaries or ORR _{BHM} \geq positive boundaries							

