7.5 SECONDARY OBJECTIVE ANALYSIS

7.5.1.1 Main analysis

There is no key secondary analysis as no key secondary endpoint has been specified in the protocol.

7.5.2 (Other) secondary objective analysis

Descriptive analysis of the following pharmacokinetic parameters will be performed for BI 905711 in phase Ia and phase Ib as outlined in section 7.3.5 in CTP and according to BI standards if applicable and feasible

- C_{max}: maximum measured concentration of BI 905711 in plasma
- AUC_{0-t2}: area under the concentration-time curve of BI 905711 in plasma

Phase Ia:

The Objective response will be analyzed the same way as the primary endpoint in Phase Ib.

Phase Ib:

The Number of patients with treatment emergent AEs, duration of overall response and disease control will be analyzed by descriptive statistics. Disease control rate will be analyzed the same way as ORR. Tumor shrinkage will be analyzed by descriptive statistics and by treatment. Waterfall and spider plots will be provided.

As of March 2023 the study was terminated due to lack of efficacy signal and it was decided to produce an abbreviated report for CTR. The abbreviated CTR would include primary and secondary endpoint analyses. There would be limited analyses provided from statistics and programming for PK and this would only include listing of consistency checking PK data. The PK group (TMCP) would provide analyses for Cmax and AUC.

Additional PK analysis

The analysis of standard PK parameters is performed according to BI internal standards (2).

Attainment of steady state

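### Phase Ib tumour shrinkage is defined as an absolute difference, so its by-arm summary depends on baseline tumour size and is not on the percent scale that the protocol quotes

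*SAP*

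**What the plan says.** SAP 5.2.2 lists radiological shrinkage among the Phase Ib secondary endpoints. It is "defined as the difference between the minimum post-baseline sum of longest diameters of target lesions and the baseline sum of longest diameters". Both sums cover one set of lesions, measured under RECIST 1.1. Protocol 2.1.3 and the synopsis use the same definition. None of these places divides by the baseline sum or names a unit.

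SAP 7.5.2 gives the analysis: "Tumor shrinkage will be analyzed by descriptive statistics and by treatment. Waterfall and spider plots will be provided". It does not say whether the table or either plot shows absolute or percentage change.

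Protocol 1.2, describing Phase Ia, uses percentages only. It says that "1 CRC patients in 2.4 mg/kg dose group achieved 21.2% tumor shrinkage" and that two non-CRC patients in the 0.6 and 4.8 mg/kg "dose groups achieved >10% tumor shrinkage".

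Protocol 7.7 plans "up to 15 CRC patients per each dose group for up to 4 cohorts". SAP sections 4 and 7.5.2 keep the secondary endpoint analyses in the abbreviated report that follows termination, so this endpoint is still due to be reported.

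**The concern.** A difference between two sums of diameters is a length. The same proportional shrinkage gives a large number in a patient with bulky disease and a small one in a patient with little measurable disease. A by-arm table of that quantity therefore mixes two things: the change under treatment and the tumour burden that patients had on entry. With at most 15 patients per CRC arm, and no stratification by tumour size described in protocol 7.6, baseline burden can differ between arms by chance.

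The scale also differs from the one on which the sponsor quotes shrinkage in protocol 1.2. A reader who sets the Phase Ib table beside those percentages would be comparing unlike quantities. If the waterfall and spider plots are meant to show percent, the written definition would not match the output.

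**Working it through.** **Inputs**
- Definition: minimum post-baseline sum (M) minus baseline sum (B), from protocol 2.1.3 and SAP 5.2.2.
- Phase Ia shrinkage: 21.2% in one CRC patient, from protocol 1.2.
- Arm size: up to 15 CRC patients, from protocol 7.7.
- Baseline sums: not given in the documents. Assumed here at 20, 50, 100, 150 and 200 mm.

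The 21.2% cannot be rebuilt, because neither of its two sums is reported.

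**Formulas**
- As defined: D = M − B.
- Percentage change: P = 100 × (M − B) / B.
- Hence D = P × B / 100.

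**One proportional effect, different baselines**

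| Assumed baseline (mm) | D for P = −21.2% (mm) | P for D = −10 mm |
|---|---|---|
| 20 | −4.2 | −50% |
| 50 | −10.6 | −20% |
| 100 | −21.2 | −10% |
| 150 | −31.8 | −6.7% |
| 200 | −42.4 | −5% |

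The same 21.2% spans a tenfold range in millimetres, because the assumed baselines do.

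**The order of two patients can reverse**
- Patient A: 20% shrinkage from 50 mm gives 0.20 × 50 = 10 mm.
- Patient B: 10% shrinkage from 150 mm gives 0.10 × 150 = 15 mm.
- In a 15-patient arm mean, A contributes 10/15 = 0.67 mm and B contributes 15/15 = 1.0 mm, although A's proportional shrinkage is twice B's.

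**Illustrative simulation (all inputs assumed)**

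There were 20,000 runs of four arms of 15. Percentage change had the same distribution in every arm (mean −10%, SD 20%). Baseline was log-normal with a median of 80 mm.

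| Log-SD of baseline | Runs in which the arm with the largest mean shrinkage differs between scales | Largest / smallest arm-mean baseline (median over runs) |
|---|---|---|
| 0.3 | 18.5% | 1.17 |
| 0.6 | 34.7% | 1.40 |
| 0.9 | 45.9% | 1.71 |

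The arms have the same true effect, so this shows only that the two scales order chance differences differently. It is not an error rate for the trial.

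**The case against.** Several points on the other side stand.

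- **The wording may be loose rather than wrong.** The definition names no unit, and the only shrinkage figures in the protocol are percentages, so the sponsor may already intend percent. But a plain difference is what is written, and following RECIST 1.1 does not by itself put this endpoint on a percent scale.
- **Some text cannot be seen.** The content of SAP section 9 is not available, and SAP 6.1 refers to a separate technical document. A percent definition could be there. The visible reference to section 9.1 (in SAP 5.1) covers objective response and PFS only.
- **Summaries are not confined to the mean.** SAP section 7 reports the median by default and prefers quantiles where data are extreme. This limits the pull of a few large tumours. It does not remove the dependence on baseline size, since a median in millimetres is still in millimetres.
- **The CRC arms are randomised.** Imbalance in baseline size arises only by chance, not systematically.
- **Little rests on the result.** Protocol 7.2 plans no hypothesis test. Protocol 7.3.1 compares doses on response rate and PFS4, and the futility provision in 7.4 names response, PFS and PD-modulation.

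A reader might infer that Phase Ib shrinkage cannot be compared with Phase Ia at all. The documents do not support that: percentage change follows from the same two sums per patient. The Phase Ia percentages are background figures on three patients, and shrinkage is not a Phase Ia endpoint. A reader might also infer that the choice of dose would be distorted, but no visible dose rule uses this endpoint.

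**Conclusion.** The point holds on the visible text. As defined, Phase Ib shrinkage is an absolute difference, its by-arm summary depends on baseline tumour size, and it is not on the scale used in protocol 1.2. On assumed baselines of 20 to 200 mm, a 21.2% shrinkage ranges from 4.2 to 42.4 mm. That range illustrates the dependence and does not estimate anything in the trial.

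The size is modest: the effect is on how a descriptive secondary endpoint reads, not on a test or a dose decision. The conclusion assumes that no percent definition sits in the SAP text that is not available. If one does, SAP 5.2.2 still needs to agree with it.

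**What to change.** In SAP 5.2.2, define tumour shrinkage as best percentage change from baseline: 100 × (minimum post-baseline sum − baseline sum) / baseline sum. In SAP 7.5.2, state that the descriptive table, the waterfall plot and the spider plot are in percent; the spider plot would show percentage change from baseline at each assessment. Keep the absolute difference as a supplementary listing, so that the quantity in protocol 2.1.3 is still reported and no protocol amendment is needed.

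Add one sentence on missing data. Under protocol version 7.0 (section 5.1), the case report form takes only overall response and progression, so sums of diameters may be missing for later assessments on either scale.

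The cost is a few lines in the SAP and the matching output specifications. The percentage needs no data beyond the two sums that the definition already requires.
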